4 SUBJECT SELECTION

4.1 Patient Selection-Criteria for Eligibility

Subjects enrolled in the AF-FLOW Registry should be selected from the investigators' general patient population with a history of atrial fibrillation that meet eligibility criteria. Patient selection may also be performed by review of the medical records of those subjects who have had prior AF treatment with ablation therapy. Investigators are responsible for screening all potential subjects and selecting those who meet the eligibility criteria for the study.

4.2 Study Inclusion Criteria

Subjects must meet ALL the following criteria:

1. Suitable candidate for intra-cardiac mapping and ablation of arrhythmias.
2. Above eighteen (18) years of age or of legal age to give informed consent specific to state and national law.
3. History of documented symptomatic atrial fibrillation.

4.3 Study Exclusion Criteria

Candidates will be excluded from the study if any of the following apply:

1. Subjects who are not candidates for cardiac ablation procedures.
2. Pregnant or nursing.
3. Presence of anatomic or comorbid conditions, or other medical, social or psychological conditions that, in the investigator's opinion, could limit the subject's ability to participate in the clinical investigation or comply with follow-up requirements.

5 DATA COLLECTION

5.1 Informed Consent

All subjects who meet all inclusion criteria and agree to participate in the AF-FLOW Registry will be asked to sign an Informed Consent Form after an explanation of the risks and potential benefits have been provided. Informed consent must be obtained from each subject prior to conducting any study related procedures including screening procedures that are not part of the standard of care at the institution.

5.2 Baseline Data

Subject source data will be collected per the relevant worksheets, medical reports, procedural reports, lab reports and any other original document in the study subject's chart. In case of electronic source data, accessible without audit trail, printouts have to be produced, verified, and confirmed. Source data will be transferred to CRFs.

After eligible subjects have signed an informed consent form and before the scheduled interventional procedure, subjects will undergo a baseline evaluation. This evaluation may be conducted in accordance with the hospital's standard of care procedures.

The evaluation will include but not limited to the following:

- Medical History and Physical Exam:
 - Subject Demographics
 - Baseline Physical Assessment
 - Height and weight
 - Resting blood pressure
 - Resting heart rate
 - Medical History

- History and documentation of AF
- NYHA score
- CHA₂DS₂-VASc score
- Cardiovascular or other medical history as it pertains to eligibility criteria
- Smoking history
- Medication History
 - Class I-IV AAD history, current doses and/or failure or intolerance
 - Other: Anticoagulants and other cardiac medications
- Baseline Imaging
 - Baseline imaging to rule out LA/LAA thrombus may be done at time of procedure or up to 48 hours prior to the start of any study procedure; however, if any evidence of left atrial thrombus is discovered, the ablation procedure will not be performed at that time. The subject may either be excluded from the study or maintained on oral anticoagulation for an additional period of time (at investigator's discretion). Repeat imaging to rule out thrombi will be required prior to study procedure.
 - A new echocardiogram (transthoracic or transesophageal) should be performed prior to ablation procedure if one has not been performed within six months of the enrollment procedure or if previous data is not available.

5.3 Pre-Procedure Requirements

Subjects should stop all AADs 48 hours prior to the procedure and be appropriately anticoagulated.

Regular amiodarone use should be discontinued at least 1 month prior to the index ablation procedure and not restarted after the ablation procedure.

5.4 General Procedural Recommendations

The ablation procedures (including patient preparation, fluid, ACT, and access site management) should be performed per the institution's standard EP lab protocol. All procedure logistical data, ablation parameters, procedural outcomes, and adverse events, will be recorded throughout the procedure. Prophylactic administration of intravenous diuretics during or after the procedure is allowed and will not be considered an adverse event.

5.5 EGF Procedure

The procedure should begin by verifying the effectiveness and durability of the prior PVI for redo subjects or a complete PVI for de novo subjects. Adenosine or isoproterenol may be administered following the PVI to detect dormant reconnections. If pharmacologic challenge is not used to detect dormant reconnections, a 20-minute wait following the last RF application for PVI should be performed. A commercially available, 64-electrode basket catheter will be introduced into both the right and left atria and unipolar electrograms from the basket catheter will be recorded for one minute each. Recordings are then analyzed with the Ablamap Software. If no sources are seen, or only sources below threshold are detected, the basket should be repositioned until the physician is confident adequate endocardial anatomical coverage has been achieved. If sources above threshold

[figure not shown]
are seen, the patient proceeds to ablation. For those subjects that have no identifiable sources or sources below threshold, the investigator may choose to ablate those subjects per their standard ablation practices.

Once the baseline (i.e., post PVI/PVI touch up) EGF maps are complete, the targeted AF source ablations will be determined according to the results of the EGF analysis using a pre-specified threshold. Ablations should be performed using standard, commercially available ablation catheters/systems. 3D-electroanatomical mapping of both atria will be performed using standard, commercially available mapping systems.

High density bi-atrial voltage mapping using a commercially available multipolar diagnostic mapping catheter during the ablation procedure is required and will be collected for analysis.

EGF mapping should be repeated in the RA and the LA until no further EGF sources above threshold are identified. If AF persists after completion of ablations, cardioversion should be performed.

Figure 2. Workflow for portion of procedure involving EGF-Guided ablation following pulmonary vein isolation

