3.6 Statistical Analysis

The primary efficacy endpoint of this registry is the successful elimination of significant sources of excitation. Target parameter is the activity of the leading source. According to the retrospective data analyzed previously, the critical threshold for significance of a source is an activity of 26%.

Significance of the leading source will be tested in each patient at multiple times, in every procedure performed, in both atria, before and after PVI or PV touch-up and before and after ablation. The effect of targeted ablation will be statistically analyzed by determining the rate of reduction of leading source activity below threshold upon ablation. If an ablation is not successfully reducing the activity or if the location of the leading source changes upon ablation, ablation will be repeated.

The secondary endpoint of the study is freedom from documented episodes of AF recurrence following the blanking period (90 days post ablation) through 12 months.

We will analyze the level of significance of this difference based on the patients with sources above threshold that were successfully ablated and remained AF free versus those patients where no sources or sources below threshold were seen but were not ablated.

Descriptive summary statistics for continuous variables will include the number of subjects, mean, standard deviation or standard error, median, minimum, and maximum. Nominal categorical variables will be summarized using counts and percentages. Ordinal variables may be analyzed as if they were continuously scaled. Subject disposition, the number and percentage of subjects who complete and discontinue as well as reasons for early discontinuation will be presented. Demographic and baseline characteristics will be summarized descriptively.

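### Section 3.6 does not say whether source-negative subjects who receive discretionary ablation under Section 5.5 belong in the secondary comparator; on one reading, operator choice after the map selects that group

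*Combined protocol and SAP*

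**What the plan says.** Section 3.6 gives the secondary endpoint as "freedom from documented episodes of AF recurrence following the blanking period (90 days post ablation) through 12 months". It then commits to assessing the significance of a difference between "patients with sources above threshold that were successfully ablated and remained AF free" and a second group, introduced by "versus those patients where no sources or sources below threshold were seen but were not ablated". On the dividing line between groups it states that "the critical threshold for significance of a source is an activity of 26"%.

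Section 5.5 gives the order of events. The procedure opens by "verifying the effectiveness and durability of the prior PVI for redo subjects or a complete PVI for de novo subjects". The atria are then mapped, and "Once the baseline (i.e., post PVI/PVI touch up) EGF maps are complete", targets are chosen from the EGF result. Subjects with a source above threshold go on to ablation. For the rest: "For those subjects that have no identifiable sources or sources below threshold, the investigator may choose to ablate those subjects per their standard ablation practices".

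The text sets no criteria for that choice, does not ask for the reason to be recorded, does not assign source-negative but ablated subjects to an analysis group, and plans no adjustment or sensitivity analysis for it. Section 5.4 does require ablation parameters and procedural outcomes to be recorded, and Section 5.7 says that ablation procedural data will be collected.

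**The concern.** The condition that closes the comparator definition in Section 3.6 is one that Section 5.5 leaves to the investigator, who decides with the EGF result in hand. This is the only between-group significance test in the plan, and it concerns the only 12-month efficacy endpoint. Two analysts working from the same database could build different comparators, both defensibly. If the choice were made after outcomes are known, it would be post hoc.

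Selection on a post-map decision can also move the comparator's AF-free rate. Eligibility (Section 4.2) does not restrict AF type, and the Introduction's own 12-month figures differ widely by type. If the decision to add lesions is related to AF type, the subjects left as not ablated will not represent source-negative subjects as a whole.

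**Working it through.** **The two readings.**

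| Source-negative subject | 'Not ablated' describes the patient | 'Not ablated' describes the source |
|---|---|---|
| PVI or touch-up only | in | in |
| No source seen, extra lesions given | out | in |
| Sub-threshold source seen, extra lesions elsewhere | out | in |
| Sub-threshold source itself ablated | out | out |

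On the patient reading, every subject given discretionary lesions leaves the comparison. On the source reading, operator choice matters only in the last row, but the group pools two kinds of treatment. On either reading the term needs a qualifier: Section 5.5 calls for a complete PVI in de novo subjects before the map, so taken literally no de novo subject is unablated. It has to mean nothing beyond PVI or touch-up, and Section 3.6 does not say so.

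**Scale on the patient reading (illustration only).** The plan gives no alpha, power, effect size or group sizes for this comparison, so there is no figure of its own to reproduce.

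Inputs from the Introduction: 12-month AF freedom of 81.6% for paroxysmal AF and 51% to 60% for persistent AF. Assumptions: source-negative subjects are half paroxysmal and half persistent, these general rates apply to them, and the discretionary ablation itself has no effect.

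Comparator rate = sum(share kept × rate) / sum(share kept).

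Whole source-negative group:
- persistent at 51%: (81.6 + 51)/2 = 66.3%
- persistent at 60%: (81.6 + 60)/2 = 70.8%

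If 20% of paroxysmal and 80% of persistent subjects are ablated, the shares kept are 0.4 and 0.1:
- (0.4 × 81.6 + 0.1 × 51)/0.5 = 75.5%, a shift of +9.2 points
- (0.4 × 81.6 + 0.1 × 60)/0.5 = 77.3%, a shift of +6.5 points

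Other patterns:

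| Ablated: paroxysmal / persistent | Shift in comparator rate |
|---|---|
| 50% / 50% | 0 |
| 40% / 60% | +2.2 to +3.1 points |
| 20% / 80% | +6.5 to +9.2 points |
| 80% / 20% | −6.5 to −9.2 points |

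**Precision.** Half of the group is lost in every row. Assume that 30 to 60 of the 100 subjects are source-negative. The comparator then falls to 15 to 30. With half-width = 1.96 × √(p(1 − p)/n) and p = 0.688:
- n = 60: 11.7 points; n = 30: 16.6 points
- n = 30: 16.6 points; n = 15: 23.4 points

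The 95% half-width therefore widens from about 12–17 points to about 17–23 points, even where there is no bias.

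**The case against.** The strongest reply is grammatical. In the Section 3.6 sentence the verbs attach most naturally to sources, and the ablation allowed in Section 5.5 follows the investigator's standard practice and is not aimed at sub-threshold sources. On that reading most source-negative subjects stay in and the map largely decides membership. This stands. A reader might infer that operator habit sets the comparator whichever way the sentence is read; the documents do not support that.

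A reader might also infer that the comparator is biased towards good prognosis. Nothing in the documents says that investigators preferentially ablate poor-prognosis subjects. The mix and the choices above are assumed, the sign reverses when the pattern does, and every shift shown is smaller than the half-width of the reduced comparator.

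Third, redefining the comparator does not make the contrast an estimate of the effect of EGF-guided ablation. The groups are not randomised and differ in substrate: the Introduction says that sources active more than a quarter of the time predict recurrence. The ablated side is conditioned on the outcome itself. A source-negative label also depends in part on the operator, since Section 5.5 has the basket repositioned until the physician is satisfied with coverage. All of this stands and limits what the repair can achieve.

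It can also be said that the lesions are recorded anyway and that this is a real-world registry. Recording lesions does not say which group a subject belongs to, and a registry that commits to a significance test still has to define its groups. The case report form is not among the documents and the Figure 2 workflow is not shown, so the split may already be derivable from the data.

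**Conclusion.** The point holds as a conflict between Sections 3.6 and 5.5 that leaves the secondary comparator without a unique definition. On the patient reading, following the plan as written selects the comparator on a decision made after the map. On the source reading, it pools different treatments without separating them. This is more than missing detail, because the two readings analyse different subjects.

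Neither the direction nor the size of any bias can be derived from the documents. The illustrated range, from −9.2 to +9.2 points with 0 if the choice is unrelated to prognosis, rests on the assumed 50/50 mix, the assumed operator patterns, the Introduction's general rates, and no effect of the extra lesions. The primary endpoint is not affected. No view is taken on whether source-negative subjects should be ablated.

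**What to change.** In Section 3.6:

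1. Define the source-negative group by the post-PVI or post-touch-up EGF map and the 26% threshold alone, and keep all such subjects whether or not further ablation was given.
2. Report that group overall, then split into PVI/touch-up only and additional discretionary ablation. Use the procedural data already collected under Sections 5.4 and 5.7. If these do not identify the split, add one procedure-form field: any lesion beyond PVI or touch-up, yes/no and type.
3. Label the contrast non-randomised and descriptive.
4. Repair the separate condition in the same sentence that restricts the ablated group to patients who stayed free of AF. Until that is done, the comparison cannot be interpreted however the comparator is defined.

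Make the change before outcomes are analysed. For the comparator, the cost is a reworded sentence, one extra table split and at most one form field. The downside is that the overall source-negative group has mixed treatment, which the split makes visible. Section 5.5 and the primary endpoint stay as they are.

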1. INTRODUCTION

[figure not shown]
Atrial fibrillation (AF) is the most common cardiac arrhythmia and is associated with increased mortality, morbidity and impaired quality of life. Catheter ablation has become the standard of care for symptomatic patients with drug-refractory AF and the cornerstone of ablation remains the electrical isolation of the pulmonary veins (pulmonary vein isolation = PVI).¹ For patients with paroxysmal AF, long-term effectiveness of an approach based on PVI as the sole ablation strategy is reported to be 81.6% at 12 months, 73.8% at 24 months, and 68.1% at 36 months post-ablation.² However, the success rate of PVI for patients with persistent AF is significantly lower with rates of freedom from AF at 12 months post-ablation ranging from 51 up to 60% regardless of the catheter ablation strategy, addition of antiarrhythmic drugs, use of cryoballoon v. RF ablation, or lesion set performed.³⁻⁶ This ceiling of efficacy in the persistent AF population may be attributable to the complex functional mechanisms of AF contributing to an individual patient's disease state.

Beyond the pulmonary vein triggers, the development and persistence of AF depends upon a localized source—a trigger or driver as well as susceptible substrate, such as re-entrant circuits and or regions of fibrotic atrial myocardium with abnormal conduction properties.^{1,7,8} After pulmonary vein isolation has been performed, accurate, enhanced mapping techniques that can localize extra-PV drivers/triggers is needed to further guide the next step in the ablation strategy.

Efforts to hone in on AF mechanisms underlying persistent AF have multiplied and several different methods for identifying these localized sources have been put forth using global or panoramic mapping techniques.⁹⁻¹² However, due to the chaotic nature of the intracardiac electrograms (EGMs) characteristic of AF, identifying active focal sources relevant to the initiation and maintenance of AF has remained challenging.

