5.8 Schedule of Events

The tests and measurements to be conducted at baseline, during the treatment procedure, and during follow-up visits are illustrated in the following chart:

Schedule of Events

Schedule of Tests:	Baseline Assessment	Index Ablation Procedure	Discharge	12 Months (+/- 45 days)
Informed Consent	X	--	--	--
Eligibility Criteria	X	--	--	--
Pre-ablation Cardiac MRI*	X	--	--	--
High Density Voltage Map(s)	--	X	--	--
Medical History and Demographics	X	--	--	--
Baseline Physical Exam	X	--	--	--
Medication Assessment	X	X	X	X
ECG	X	--	X	X
Adverse Events	--	X	X	X
Procedural Data	--	X	--	--
Protocol Deviations	X	X	X	X

*If performed as part of the investigator's standard of care.

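### Mandatory bi-atrial voltage maps have no fixed timing in the text and no role in section 3.6, so the unadjusted secondary 12-month comparison stays open to plausible confounding by atrial substrate

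*Combined protocol and SAP*

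**What the plan says.** Section 5.5 (EGF Procedure) requires the measurement and gives it a purpose: "High density bi-atrial voltage mapping using a commercially available multipolar diagnostic mapping catheter during the ablation procedure is required and will be collected for analysis". The schedule of events in section 5.8 lists the voltage map at the index procedure without condition. The pre-ablation cardiac MRI, by contrast, is needed only where it is local standard of care.

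The introduction gives a reason to care about substrate. It says AF depends on a localized source, described as a trigger or driver, together with "susceptible substrate, such as re-entrant circuits and or regions of fibrotic atrial myocardium with abnormal conduction properties".

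Section 3.6 (Statistical Analysis) contains two analyses. For the primary endpoint, "Target parameter is the activity of the leading source", assessed before and after ablation. For the secondary endpoint, "We will analyze the level of significance of this difference", and the groups are "patients with sources above threshold that were successfully ablated and remained AF free versus those patients where no sources or sources below threshold were seen", the latter described as not ablated. No model and no covariate is named. Baseline characteristics are to be summarized descriptively. Voltage, scar, low-voltage area and substrate do not appear in the section.

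**The concern.** The registry imposes an invasive measurement in both atria for the sake of analysis, and the analysis section does not say what that analysis is. This matters most in the one between-group test. Subjects are sorted by whether the mapping software found sources above threshold, not by randomisation. If those with such sources also tend to have more diseased atria, and diseased atria recur more often, a difference at 12 months would mix the effect of sources and their ablation with the effect of substrate. If the imbalance runs in that direction, the bias counts against the source-ablated group and could hide a real benefit.

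Timing decides whether the maps can be used to address this. A map made after source ablation would show fresh lesions as low voltage, mainly in subjects who had sources to ablate, so the measurement error would follow the grouping variable. If acquisition time is not recorded during the study, this may not be recoverable later.

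**Working it through.** The plan gives no significance level, power, effect size or sample-size derivation, so there is no figure to reproduce. The check has two parts.

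**1. Text**

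- *Timing.* Section 5.5 opens with: "The procedure should begin by verifying the effectiveness and durability of the prior PVI for redo subjects or a complete PVI for de novo subjects". EGF mapping, source ablation and repeat EGF mapping follow. The voltage map is placed only within the procedure as a whole, so the text allows it before PVI, after PVI but before source ablation, or after source ablation. Section 5.8 does not split these. Figure 2, the workflow after PVI, was not available.
- *Use.* Section 3.6 defines no variable, cut-off, summary or covariate from the maps. Its general sentences on descriptive statistics could cover such a variable but do not define one.
- *Which analysis is exposed.* The primary analysis compares leading-source activity before and after ablation in the same patient, so imbalance in substrate between groups does not confound it in this way. The secondary analysis compares different patients.
- *Group definition.* As worded, the first secondary group contains only subjects who stayed AF free. Read literally, its AF-free rate is 100% by construction, and no covariate can repair that. Section 5.5 also lets investigators ablate subjects without above-threshold sources, whereas section 3.6 describes them as not ablated.

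**2. Illustrative size, with groups defined by source status only**

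Formula: spurious difference = (prevalence of poor substrate in group 1 − prevalence in group 2) × (AF-free rate with good substrate − AF-free rate with poor substrate).

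Inputs:
- Good substrate: 81.6%, the introduction's 12-month figure for paroxysmal AF after PVI.
- Poor substrate: 51% or 60%, the ends of the introduction's range for persistent AF.
- Using these rates as stand-ins for substrate is an assumption.
- The prevalences are assumed; the documents give none.

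| Prevalence, group 1 v 2 | Poor-substrate rate 51% | Poor-substrate rate 60% |
|---|---|---|
| 30% v 20% | 0.10 × 30.6 = 3.1 points | 0.10 × 21.6 = 2.2 points |
| 50% v 25% | 0.25 × 30.6 = 7.7 points | 0.25 × 21.6 = 5.4 points |
| 60% v 20% | 0.40 × 30.6 = 12.2 points | 0.40 × 21.6 = 8.6 points |

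For example, at 60% v 20% and 51%, the AF-free rates are 0.6 × 51 + 0.4 × 81.6 = 63.2% and 0.2 × 51 + 0.8 × 81.6 = 75.5%.

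With 100 subjects and a two-sided 0.05 test (normal approximation, counting only rejections in the direction of the imbalance), these differences would be declared significant in about 4% to 26% of trials with a 50/50 split and 4% to 21% with a 70/30 split. For scale, 100 subjects give 80% power only for a rise of about 26 points (50/50) or 28 points (70/30) from 55%. The main risk is therefore a biased estimate rather than a frequent false-positive result.

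**The case against.** The case for leaving this alone has real weight.

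- *Purpose.* No passage calls the voltage map a substrate measurement or ties it to the 12-month comparison. A reader might infer that the maps were collected for adjustment and then forgotten; section 5.5 says only that they are for analysis. This stands, so the point is that the role is undefined, not that a stated role was dropped.
- *Substrate as a driver.* A reader might take the introduction to name substrate as a driver of AF. It places substrate beside the trigger or driver. This stands.
- *Confounding.* No data in the documents link voltage to source presence or to recurrence. Confounding is an inference from the stated rationale. This stands, and the size above is hypothetical.
- *Timing.* Figure 2 may show an order, so the timing point reaches only the text and schedule. Even if the figure shows one, the text and CRF should carry it.
- *Other defects come first.* Section 3.6 adjusts for nothing, and the first group is selected on the outcome. Adding voltage alone would not rescue the comparison. This stands and shapes the fix. It does not excuse leaving a required measurement without a definition or a use.

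**Conclusion.** The point holds in a limited form. Voltage mapping is required for analysis, its timing relative to lesions is not fixed in the text or schedule, and section 3.6 does not use it. The secondary comparison is non-randomised and unadjusted, and the protocol's own rationale makes substrate a plausible confounder of it. The hypothetical bias is about 2 to 12 points. That range rests on the paroxysmal and persistent rates standing in for good and poor substrate and on assumed prevalence differences of 10 to 40 points; an imbalance the other way would reverse the sign.

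Two stronger readings are not supported. One is that the registry's efficacy result as a whole is confounded: the primary endpoint is a within-patient measure and is not touched. The other is that adjusting for voltage would by itself make the secondary comparison valid: it would not while one group is defined by having stayed AF free.

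The change is worth making because it is cheap, uses data already required, and depends on timing being recorded as maps are made.

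**What to change.** 1. **CRF.** Add one field for each voltage map: acquired before PVI, after PVI but before source ablation, or after source ablation.
2. **Low-voltage variable.** In the SAP, define percent low-voltage area at a single cut fixed in advance, using only maps made before source ablation. Where the map follows PVI, exclude the PVI lesion region, since fresh PVI lesions would otherwise count as low voltage.
3. **Secondary groups.** Define them by source and ablation status only, with AF freedom as the outcome and not as an entry condition. Reconcile section 3.6, which describes the comparison subjects as not ablated, with section 5.5, which permits their ablation.
4. **Analysis.** Name the model for 12-month AF freedom, and report the group difference unadjusted and adjusted for low-voltage area, each with a 95% CI. Use one combined bi-atrial covariate, or two if the atria are kept separate, and say which in advance.
5. **Missing maps.** Report how many subjects have only maps made after source ablation, and give the unadjusted difference in the subjects who enter the adjusted model as well, so that the two estimates can be compared.

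Cost: SAP wording, one CRF field, off-line analysis of maps already required, and one or two model parameters in at most 100 subjects. Subjects with only post-source-ablation maps will lack the covariate. They will come mainly from the source-ablated group, which is why their number must be shown.
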